6.11.3. Deaths

Incidences of deaths are to be reported, along with the primary cause of death in a summary table. All deaths including on-study death (deaths that occurred within 28 days of treatment discontinuation) and primary cause of death will be presented in a patient listing.

6.11.4. Clinical Laboratory Evaluations

Blood samples for the following clinical laboratory tests were collected and analyzed for safety:

- Hematology: hemoglobin, hematocrit, platelet count, red blood cell count, and white blood cell (WBC) count with differential (neutrophils, lymphocytes, monocytes, eosinophils, and basophils)
- Serum chemistries (nonfasting): alkaline phosphatase, albumin, ALT, AST, blood urea nitrogen, total cholesterol, creatinine, glucose, lactate dehydrogenase, total and direct bilirubin, total protein, sodium, potassium, calcium, chloride, bicarbonate, magnesium, phosphate, and urea
- Coagulation: prothrombin time (PT), activated partial thromboplastin time (aPTT), and prothrombin international normalized ratio (INR)
- Thyroid panel: thyroid-stimulating hormone/thyrotropin (TSH), free triiodothyronine (T3),

and free thyroxine (T4)

Additional laboratory tests include:

- Urine chemistry: protein, glucose, blood, leukocyte esterase, specific gravity, pH, and ketones
- Biochemical response markers: carcinoembryonic antigen (CEA), calcitonin, and thyroglobulin
- Adrenocorticotrophic hormone (ACTH)/cortisol

Whenever defined, laboratory values will be assigned toxicity grades based on CTCAE Version 5. For some laboratory tests, these criteria may include qualifying definitions (e.g. clinical AE and/or requirement for concomitant medication) in addition to the specific laboratory value used for the definition of the toxicity grades. For such tests, the qualifying definitions will not be used for the assignment of toxicity grades.

The maximum or “worst” change in each laboratory value occurring during treatment will be assessed by means of shift tables showing the number and proportion of patients with directional shifts in CTCAE grades relative to baseline. For laboratory variables without CTCAE toxicity grades (such as thyroid function), similar tables will be constructed showing shifts to outside (above or below) the local laboratory normal range relative to baseline. Baseline lab values will also be summarized in a descriptive manner.

6.11.5. Vital Signs and Other Physical Findings

The following vital signs and other physical findings were measured at screening and at periodic time points (including end of treatment and safety follow-up) following the initiation of selpercatinib:

- body weight (kg)
- systolic and diastolic blood pressures (mmHg)
- body temperature (degrees Celsius)
- respiration rate (breaths per minute)
- heart rate (beats per minute)
- ECOG performance status

The parameters and shift from baseline will be summarized by cycle for the safety population. A patient-level listing of vital signs will be provided.

6.11.6. Electrocardiograms (ECG)

ECG results will be summarized by cycle for the safety population.

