As of March 30, 2020, a total of 734 of the 744 patients (98.7%) treated in LIBRETTO-001 experienced at least 1 TEAE (regardless of relationship to study drug) of any grade. The TEAEs were coded according to the Medical Dictionary for Regulatory Activities (MedDRA) system organ class (SOC). Across 9 dose levels ranging from 20 mg QD to 240 mg BID in these 744 patients, TEAEs occurring in $\geq 15\%$ patients were: dry mouth (39.7% total; 35.2% related), diarrhea (38.2% total; 21.8% related), hypertension (36.3% total; 25.1% related), AST increased (31.9% total; 25.9% related), ALT increased (31.5% total; 25.9% related), fatigue (30.8% total; 19.2% related), constipation (26.6% total; 12.8% related), edema peripheral (25.3% total; 14.1% related), nausea (23.3% total; 10.1% related), headache (23.3% total; 8.6% related), blood creatinine increased (20.2% total; 11.6% related), abdominal pain (19.5% total; 5.9% related), rash (18.1% total; 11.3% related), electrocardiogram QT prolonged (17.5% total; 13.6% related), cough (15.9% total; 1.1% related), vomiting (15.9% total; 4.3% related), and dyspnea (15.2% total; 1.6% related).

A total of 441 (59.3%) patients across all dose levels in LIBRETTO-001 had Grade 3-4 TEAEs. Grade 3-4 TEAEs that were considered to be related to study drug were reported in 239 (32.1%) patients across all dose levels. TEAEs included hypertension (19.0%; 12.1% related), ALT increased (9.8%; 8.1% related), AST increased (7.8%; 6.0% related), hyponatremia (5.8%; 0.4% related), ECG QT prolonged (4.0%; 2.8% related), lymphopenia (4.0%; 1.1% related), diarrhea (3.5%; 1.6% related), thrombocytopenia (2.8%; 2.0% related), and pneumonia (2.8%; none

related), dyspnea (2.6%; none related), neutropenia (2.4%; 1.5% related), anemia and hypocalcemia (each 2.2%, each 0.4% related), and hypophosphatemia (2.2%, 0.1% related). All other Grade 3-4 TEAEs occurred in less than 2% of patients overall. Overall, 32 (4.3%) patients have died within 28 days of the last dose of study drug, and no deaths have been attributed to study drug.

Additional details are provided in the selpercatinib IB.

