- k. Obtain a single pre-dose ECG during Screening and again on C1D1. If the C1D1 pre-dose QTcF > 470 msec (QTcF = QT (msec)/RR^{1/3}), where RR (msec) = $60 \times 1000/\text{BPM}$), the Sponsor should be notified prior to dosing to determine whether the patient remains eligible. On C1D8, C2D1 and thereafter, perform a single ECG at 2 hours (± 10 minutes) post-selpercatinib dosing. On C1D8 PK collection, an extra ECG should be timed prior to the PK sample being drawn. Dose patients in the visit to ensure accuracy of timing. If any ECG demonstrates QTcF 481-500 msec, perform an additional ECG at the same day, specific time judged by investigator. If any ECG demonstrates QTcF > 500 msec, repeat the ECG twice (triplicate in total) at the same day, specific time judged by investigator, and manually review to confirm accuracy. If QTcF > 500 msec is confirmed on 2/3 ECGs, hold selpercatinib and assess for alternative causes (concomitant medications, electrolyte abnormalities). Potassium should be > 4 mEq/L and $< \text{ULN}$ and magnesium and calcium should be within normal limits. selpercatinib may be resumed at one reduced dose level when QTcF has returned to baseline value, and with continued ECG monitoring as noted in the assessment schedule.
- l. Repeat only if EOT reading showed treatment-emergent abnormalities.
- m. For women of childbearing potential: Serum pregnancy test at Screening, serum or urine pregnancy test at Day 1 of every cycle (-2 days) (surgically sterilized females or those who have not experienced menses for at least 2 years are not required to be tested i.e., post-menopausal women who have not had menses within the last 12 months but have had menses within the last 24 months will be required to have a serum pregnancy test performed.). If screening testing is performed ≤ 7 days prior to C1D1, repeat testing does not need to occur on C1D1.
- n. Hemoglobin, hematocrit, RBC count, WBC count with differential (neutrophils [count and percent] and lymphocytes, monocytes, eosinophils, basophils [percent]), and platelet count). Patients found to have treatment-emergent hematologic toxicity of Grades 3 or 4 will be monitored at least weekly until resolution. If screening testing is performed ≤ 7 days prior to C1D1, repeat testing does not need to occur on C1D1.

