8.2 Safety Assessments

8.2.1 *Electrocardiograms*

ECG monitoring should be performed as outlined in the SoA (Table 7-1). The actions below should be taken if the triplicate average QTcF is greater than 500 msec.

- Manually review to confirm accuracy
- Assess for alternative causes (concomitant medications, electrolyte abnormalities, presence of pacemaker). Potassium should be ≥ 4 mEq/L and $<$ ULN and magnesium and calcium should be within normal limits.
- Institutional guidelines or SOC measures for management of QTcF interval >500 msec and/or associated arrhythmias should be initiated.
- Clinical chemistry should be assessed and if electrolytes are abnormal, they should be repeated as indicated.

If a patient experiences a QTcF interval >500 msec and if the investigator deems it in the best interest of the patient, the patient may continue treatment with study drug (with a dose reduction).

8.2.2 **Clinical Safety Laboratory Assessments**

- Investigator sites may use local laboratories to determine patient eligibility and treatment decisions.
- In addition, blood will be collected,
 - See [Appendix H](#) for the list of clinical laboratory tests to be performed and [Table 7-1](#) (Schedule of Activities) for the timing and frequency.
 - The investigator should review any clinically significant abnormal laboratory findings and assess relevance to patient care. If the laboratory findings are clinically significant, the investigator should document the findings as an adverse event in the case report form. The laboratory reports must be filed with the source documents. Clinically significant abnormal laboratory findings are based on investigator judgement.
- Regardless of whether or not central or local laboratory tests are used to determine patient care decisions, all laboratory tests with values considered clinically significantly abnormal during participation in the study or until completion of SFU should be repeated until the values return to normal or baseline or are no longer considered clinically significant by the investigator.
 - If such values do not return to normal/baseline within a period of time judged reasonable by the investigator, the etiology should be identified, and the sponsor notified.
 - All protocol-required laboratory assessments, as defined in [Appendix H](#), must be conducted in accordance with the laboratory manual and the SoA.

8.2.2.1 **Hepatic Safety Monitoring**

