6.1.2. Definitions and Conventions

The **baseline value** is the last value observed prior to the first dose of study drug

The **study day** will be calculated in reference to the first dose date of selpercatinib as follows:

- assessment date/event date – first dose date + 1, if assessment date or event date \geq first dose date,
- assessment date/event date – first dose date, if assessment date or event date < first dose date.

Unless otherwise noted, **summaries of continuous variables** will include a mean, median, standard deviation, minimum, and maximum.

Unless otherwise noted, **summaries of categorical variables** will include the frequency and percentage (relative to the population being analyzed) of each category.

Duration is calculated as:

- Duration (days): (End date – Start date + 1)
- Duration (weeks): (End date – Start date + 1) / 7
- Duration (months): (End date – Start date + 1) / 30.4375
- Duration (years): (End date – Start date + 1) / 365.25

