6.11.2.2. Adverse Events of Special Interest

Based upon information available to date and/or known class effects of this compound, several categories of AE have been designated to be of special interest. These include the following which are discussed below:

- Hepatic effects/potential liver toxicity (elevated levels of ALT, AST, total bilirubin, direct bilirubin, and ALP)
- Hypersensitivity
- Hypertension
- Thrombocytopenia

Liver function tests will be presented using conventional summary statistics, toxicity shift table analysis, and by time-to-event plots. Possible drug-induced liver injury will be assessed as defined in FDA guidance. Hy's Law cases of drug-induced liver injury have the following components:

- The drug causes hepatocellular injury as evidenced by an elevation of ALT or AST to 3-fold or greater of the upper limit of normal (ULN) relative to control (or in this context to baseline levels)

- In addition to the transaminase increases, an associated (i.e. concomitant) elevation of total serum bilirubin to 2-fold or greater of the ULN without initial findings of cholestasis (elevated alkaline phosphatase)
- No other explanation can be found for the combination of increased transaminase(s) and total bilirubin such as viral hepatitis, pre-existing acute liver disease, or concomitant drug capable of causing the observed injury

Events of hypersensitivity will be identified using search terms that include the preferred terms *Hypersensitivity* and *Drug hypersensitivity* under the *Immune System Disorders* MedDRA system organ class.

Events of hypertension will be identified using the preferred terms *Blood pressure abnormal* and *Blood pressure increased* under the *Investigations* system organ class, as well as the preferred term *Hypertension* under the *Vascular Disorders* system organ class.

Events of thrombocytopenia will be identified using the preferred term *Thrombocytopenia* under the *Blood and lymphatic system disorders* system organ class, as well as the preferred term *Platelet count decreased* under the *Investigations* system organ class.

Additional AEs of special interest may be added based on review of the safety data before the final data extraction.

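### The SAP's ECG analysis is a by-cycle summary only, so it neither counts nor identifies patients whose measured QTcF crossed the protocol's thresholds

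*SAP*

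**What the plan says.** **ECG analysis.** SAP 6.11.6 reads in full: "ECG results will be summarized by cycle for the safety population". Under SAP 6.1.2, a continuous summary, unless otherwise noted, "will include a mean, median, standard deviation, minimum, and maximum".

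**Neighbouring sections.** SAP 6.11.4 gives laboratory values worst-on-treatment shift tables with numbers and proportions of patients. SAP 6.11.5 gives vital signs a shift from baseline and a patient-level listing.

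**Protocol thresholds.**
- QTcF above 470 msec is exclusion criterion 27. On C1D1 before dosing it also triggers sponsor notification (Table 7-1, note k).
- Note k on the next band: "If any ECG demonstrates QTcF 481-500 msec, perform an additional ECG at the same day, specific time judged by investigator".
- Note k on the top band: "If QTcF > 500 msec is confirmed on 2/3 ECGs, hold selpercatinib and assess for alternative causes".
- Section 8.2.1 frames the top band differently: "The actions below should be taken if the triplicate average QTcF is greater than 500 msec".

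**Prior experience.** Protocol 1.5 reports QT prolongation in 17.5% of patients (13.6% related). For Grade 3-4 it gives "ECG QT prolonged (4.0%; 2.8% related").

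**Special interest list.** SAP 6.11.2.2 says that "several categories of AE have been designated to be of special interest": hepatic effects, hypersensitivity, hypertension and thrombocytopenia. It then leaves the list open: "Additional AEs of special interest may be added based on review of the safety data before the final data extraction".

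**The concern.** ECG assessments are part of a secondary safety endpoint (Protocol 9.1.2). For a drug with a recognised QT signal, the main question is how many patients had marked prolongation, and which ones. That calls for one worst value per patient. A by-cycle summary describes a different unit, the set of readings at each visit, and it does not follow a patient across visits.

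The SAP also does not say whether same-day repeats and unscheduled ECGs enter the summary. This matters because the rule above 500 msec is built on those repeats. If 6.11.6 is programmed as written, the report could describe the ECG data without saying how many patients exceeded 480 or 500 msec, although every reading needed for that count is collected.

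**Working it through.** **1. The plan's own safety figure.** Protocol 9.3 and SAP 5.2 give about 80% and 98% probability of seeing at least one event in 75 patients at true rates of 2% and 5%. With P = 1 - (1 - p)^75:
- p = 0.02: P = 0.780
- p = 0.05: P = 0.979

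Both agree with the stated figures to within 2 percentage points.

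**2. Expected QT events in 75 patients.** The rates come from Protocol 1.5 (744 patients). Expected number = 75p.

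| Event | p | Expected patients | P(at least 1) | P(at least 2) | P(at least 3) |
|---|---|---|---|---|---|
| Any grade | 0.175 | 13.1 | 1.000 | 1.000 | 1.000 |
| Any grade, related | 0.136 | 10.2 | 1.000 | 1.000 | 0.999 |
| Grade 3-4 | 0.040 | 3.0 | 0.953 | 0.807 | 0.581 |
| Grade 3-4, related | 0.028 | 2.1 | 0.881 | 0.624 | 0.351 |

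On these rates, a table of patients by threshold would probably have patients in it.

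**3. What the by-cycle summary would show.** The documents give no typical QTcF, so I assume 410 to 440 msec for most patients and 520 msec for an outlier. The shift in a cycle mean from k outliers among n patients is k × (520 - typical)/n.
- n = 75, k = 1: 80/75 = 1.1 to 110/75 = 1.5 msec
- n = 75, k = 3: 240/75 = 3.2 to 330/75 = 4.4 msec
- n = 30, k = 1: 80/30 = 2.7 to 110/30 = 3.7 msec

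The mean barely moves, but the maximum for that cycle would read 520 msec in every case. The default summary can therefore reveal that at least one reading was above 500 msec. It cannot distinguish one such patient from three, or show whether the maxima in two cycles belong to the same patient. Nor can it count patients at 481-500 msec, give a change from baseline, or show whether a high reading was confirmed.

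**4. What the other planned outputs would show.**

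| Output | What it counts | What it leaves out |
|---|---|---|
| SAP 6.11.2, TEAE tables by preferred term and maximum grade | Patients with QT prolongation reported as an adverse event | Measured values not reported as an event; the msec bands |
| SAP 6.11.2.1, events leading to dose modification or discontinuation, with listings | Reported events that changed treatment | Readings that did not lead to a change |
| SAP 6.11.1.3, dose changes with reasons | Patients with reductions or omissions | QTcF itself |

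**5. The rule above 500 msec.** Note k requires confirmation on two of three ECGs and then a hold. Section 8.2.1 uses the average of three, and says the patient may continue at a reduced dose if the investigator judges that to be in the patient's interest. Two of three readings can exceed 500 msec while the average does not, and the reverse is also possible. A count of confirmed cases therefore depends on which text is programmed.

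**The case against.** The strongest reply is that the signal would not be lost. The default maximum exposes extreme values if QTcF is what gets summarised. The 17.5% and 4.0% are themselves adverse event rates, and the SAP plans the same kind of display: patients counted once at their worst grade, by preferred term, and repeated for related events. SAP 6.1.2 also defines frequency tables, so 6.11.6 does not rule out a categorical display. All of this stands. A reader might infer that QTcF outliers would go unseen, or that the report could not speak to QT risk at all; the documents do not support either reading. What remains is that no planned output commits to counting patients by measured QTcF.

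Three further inferences also go beyond the text:
- **Repeat and unscheduled ECGs are left out.** The SAP does not say so; it is silent. When a scheduled ECG is the trigger, its own value would already be in the cycle summary.
- **QT prolongation has to be an event of special interest.** The four listed categories match the drug-specific events with their own dose adjustments in Protocol 6.2.4, the list can be extended, and the preferred-term table already covers QT prolongation. Adding it is a reasonable preference, not a correction of an error.
- **A maximum over all ECGs counts dose-hold cases.** It does not, because it includes single unconfirmed readings. The 481-500 msec band triggers only another ECG.

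**Conclusion.** The point holds as a gap in the specification of a secondary safety analysis. SAP 6.11.6 does not count or identify patients who crossed the protocol's QTcF thresholds, while laboratory values and vital signs receive fuller treatment in adjacent sections. The other planned outputs reduce the consequence but do not close the gap.

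As to size, about 13 of 75 patients would be expected to have QT prolongation and about 3 (2 if related-only) Grade 3-4, with a 95% chance of at least one Grade 3-4 case (88% if related-only). This assumes that the earlier study's rates carry over. Those rates are pooled over nine dose levels from 20 mg QD to 240 mg BID, and the documents do not equate Grade 3-4 with QTcF above 500 msec, so the figures are a proxy. The primary endpoint is not affected. The change is worth making because it is cheap and answers a question that the protocol itself raises.

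**What to change.** In SAP 6.11.6:
1. Name QTcF as the analysed parameter.
2. Tabulate the number and percentage of patients by worst post-baseline QTcF, cut at the protocol's 470, 480 and 500 msec so that the 481-500 and above-500 bands are visible. State that all scheduled, repeat and unscheduled ECGs are used.
3. Summarise each patient's maximum increase from baseline. The documents give no cut-point for change, so none is required.
4. List patients with any QTcF above 480 msec.
5. Report patients with confirmed values above 500 msec separately from those with a single reading.

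Item 5 has to wait until the sponsor reconciles Table 7-1 note k with Protocol 8.2.1, both on what triggers action (two of three readings or the average of three) and on what follows (hold or continue at a reduced dose). This review takes no position on which is right.

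The cost is one or two extra tables and a listing from data already collected, with no change to study conduct.

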6.12. Subgroup Analyses

If warranted by data, the point estimates of ORR (and 95% CI) and median DOR (and range)

based on IRC and investigator assessments will be calculated for the subgroups defined by the following:

- age (< 60 years, ≥ 60 years)
- sex (male, female)
- ECOG performance status at baseline (0, 1–2)
- smoking status (never smoked, current smoker, former smoker)
- *RET* fusion gene (KIF5B/CCDC6/NCOA4, other)
- *RET* mutation type (M918T, extracellular cysteine mutation, other)
- Prior systemic therapy use (treatment naïve vs pre-treated)
- type of prior systemic therapies (MKI including *RET*, other MKI, non-MKI)
- type of prior systemic therapies 2 (anti-PD-1/PD-L1 antibody, other)
- best overall response to most recent prior systemic therapy (CR, PR, SD, PD, NE)

Treatment naïve patients include patients who received no prior systemic therapies or who received only adjuvant/neo-adjuvant therapies; Otherwise, patients are categorized as pre-treated.

As a supportive analysis, ORR will be summarized on the **response evaluable subgroup**, defined as patients with measurable disease (at least 1 target lesion) and at least 1 post-baseline tumor assessment.

6.13. Protocol Deviation

Protocol deviations will be identified throughout the study. Important protocol deviations (IPDs) that potentially compromise the data integrity and patients' safety will be summarized. These deviations will include deviations that can be identified programmatically and those that can only be identified by the clinical research associate during monitoring. IPDs are described in the Trial Issue Management Plan (TIMP) within the study Trial Master File.

After further review, a comprehensive listing of patients with major protocol deviations (MPDs) among IPDs that might have significantly affected the interpretation and integrity of data or patient safety will be provided. Patients with MPDs will be excluded from PP population.

A listing of patients with MPDs will be defined prior to database lock, and the PP population will be derived using this list. The PP population may be used for select sensitivity analyses of the efficacy data.

IPDs and MPDs will be summarized by treatment arm and by the category and subcategory of deviation.

